6. STUDY VISITS AND ACTIVITIES

6.1. Acceptable Windows for Protocol Assessments and Follow-up Visits

Unless otherwise specified in the enrollment criteria, Schedule of Activities table, and in other sections of the protocol, Table 7 serves as a general guideline for acceptable windows within which assessments and procedures are conducted and when study visits are scheduled.

Table 7 Windows for Performing Assessments and Scheduling Follow-Up Visits

PK Assessments	
Time Points	Acceptable Window
Predose	< 60 minutes prior to study drug administration
Start of study drug to < 1 hour postdose	± 5 minutes
1 hour postdose to ≤ 6 hours postdose	± 30 minutes, but the PK samples should be taken as close to the protocol stipulated times as possible
24 hours postdose	□ 3 hour prior to next dose
Study Visits	
Visit/Day	Acceptable Window
Pretreatment Visit	Scheduled within 14 days prior to randomization ^a
Cycle 1 Day 1 and 2	No window applies
Cycle 1 Day 8	± 1 day
Cycle 1 Days 15 and 16	± 1 day for Day 15; Day 16 must be the day after Day 15
Cycle 2 Day 1	± 3 days ^b
Cycle 2 Day 15	± 1 day
Cycle 3 Day 1	± 3 days ^b
Ongoing Visits	Every 28 days (± 3 days) ^b ; and Day 15 of each cycle (± 1 day)
Early Termination or End of Study	7 ± 1 day from date of final dose of quizartinib or site's knowledge of reason for study discontinuation

a Bone marrow assessments at Screening can be done within 14 days of randomization; bone marrow examinations outside this window may be acceptable if agreed by the Medical Monitor.

b The ± 3 day window for Cycle 2 Day 1 and Day 1 of ALL cycles thereafter allows scheduling of necessary assessments (including bone marrow aspirates and/or biopsies), obtaining test results, preparing study drug and dispensing for those subjects receiving subsequent cycles of therapy (refer to Schedule of Activities and its footnotes for exceptions). Despite this window, every effort must be made such that there are no dosing schedule interruptions for subjects on this continuous dosing regimen.

6.2. Study Visits

6.2.1. Screening Activities

Eligible subjects will be screened as outlined below. Unless otherwise specified, screening procedures must be completed within 14 days prior to randomization to determine that subjects meet inclusion criteria and do not meet exclusion criteria.

- Written informed consent
- Medical and disease history and demographics
- Physical examination
- Vital sign determinations
- ECOG performance status evaluation
- Assessment of prior and concomitant medications, including medications received within 28 days prior to screening.
- Pregnancy testing; women of childbearing potential must have a negative serum (minimum sensitivity 25 IU/L or equivalent units of hCG).
- Determination of coagulation profile (prothrombin time [PT]/international normalized ratio [INR])
- Chest X-rays (posterior/anterior and lateral)
- 12-lead ECG (triplicate)
- Collection of samples for clinical laboratory tests (hematology, chemistry, and urinalysis)
- MUGA scan or ECHO to be performed at screening on all subjects unless a scan performed within 1 month of screening revealed LVEF \geq 45%.
- Bone marrow aspiration and biopsy for central confirmation of diagnosis; biopsy may be omitted if the aspirate is considered to be adequate. If a specimen has been sent for central testing but the subject requires treatment for AML before the central FLT3-ITD test result is available, a local test result may be acceptable for randomization after consultation with the Medical Monitor. A Screening specimen must be sent to the central laboratory for confirmation, and results compared to the local test result.

In cases where subjects have been randomized and the FLT3-ITD local and central laboratory results are discordant the subjects may continue with quizartinib dosing.

- Collection of bone marrow specimen and whole blood (at approximately the same time) for FLT3-ITD testing (and other AML associated mutations) by central laboratory. If it is not feasible to obtain a bone marrow specimen at Screening, peripheral blood only may be submitted to Navigate BioPharma Services, Inc, a Novartis Company (Navigate).

- This test is approved by the FDA for investigational use and is CE marked. It is not approved by the FDA or other regulatory agencies for commercial use. The results of the test will be used to support the development of a commercial companion diagnostic test. The FDA has reviewed the methodology and assay development and validation of the companion diagnostic test, as documented by Investigational Device Exemption number G140012.

6.2.2. Schedule of Activities and Assessments for Subjects Receiving Quizartinib

6.2.2.1. Cycle 1, Day 1

The following activities will take place during this visit:

- Physical examination
- Vital sign determinations
- ECOG performance status evaluation
- Assessment of prior and concomitant medications
- A urine pregnancy test must be performed prior to dosing and every 3 months during the treatment phase in women of child-bearing potential
- 12-lead ECG (triplicate) before dosing and 2, 4, and 6 hours after dosing
- Collection of samples obtained before dosing for clinical laboratory tests (hematology, chemistry, and urinalysis)
- AE/SAE evaluation
- Collection of blood samples for PK determinations before dosing and 1, 2, 4, and 6 hours after dosing. When an ECG is performed at the same study time point, the PK specimen should be taken immediately afterwards.
- If consent is provided, collection of samples (blood [Pax gene DNA, Pax gene RNA, and PBMC] and buccal swab) should be obtained before dosing for pharmacogenomic and proteomic determinations.
- Administration of quizartinib at the study site

6.2.2.2. Cycle 1, Day 2 and Day 8 (±1 day)

The following activities will take place during these visits:

- Physical examination
- Vital sign determinations
- Review of concomitant medications
- 12-lead ECG before dosing and 2 to 4 hours after dosing
- Collection of samples obtained before dosing for clinical laboratory tests (hematology, chemistry, and urinalysis)

- AE/SAE evaluation
- Collection of blood samples for PK determinations on Day 2 before dosing and on Day 8 before dosing and 2 to 4 hours after dosing. When an ECG is performed at the same study time point, the PK specimen should be taken immediately afterwards.
- Administration of quizartinib at the study site

6.2.2.3. Cycle 1, Day 15 (± 1 day)

The following activities will take place during this visit:

- Physical examination
- Vital sign determinations
- Review of concomitant medications
- 12-lead ECG before dosing and 2, 4, and 6 hours after dosing
- ECG review to determine if dose escalation is required:
- Please refer to Section 5.6.4.3 for dosing guidelines to determine if the subject meets specified criteria for dose escalation; first increased dose to be administered Cycle 1 Day 16.
- Collection of samples obtained before dosing for clinical laboratory tests (hematology, chemistry, and urinalysis)
- AE/SAE evaluation
- Collection of blood samples for PK determinations before dosing and 1, 2, 4, and 6 hours after dosing. When an ECG is performed at the same study time point, the PK specimen should be taken immediately afterwards.
- Administration of quizartinib at the study site
- Review of returned study medication and assessment of compliance

6.2.2.4. Cycle 1, Day 16 (the day after Day 15)

The following activities will take place during this visit:

- Collection of blood sample for PK determinations before dosing
- Administration of quizartinib at the study site

6.2.2.5. Cycle 2, Day 1 (± 3 days)

The following activities will take place during this visit:

- Physical examination
- Vital sign determinations
- ECOG performance status evaluation
- Review of concomitant medications

- 12-lead ECG (triplicate) before dosing and 2 to 4 hours after dosing
- Collection of samples obtained before dosing for clinical laboratory tests (hematology, chemistry, and urinalysis)
- Bone marrow aspiration and biopsy for local determination of response; biopsy may be omitted if aspirate sufficient.
- AE/SAE evaluation
- Collection of blood samples for PK determinations before dosing and 2 to 4 hours after dosing. When an ECG is performed at the same study time point, the PK specimen should be taken immediately afterwards.
- Administration of quizartinib at the study site
- Review of returned study medication and assessment of compliance
- Consideration of whether a dose escalation is required if it did not occur at Day 16 (following results from bone marrow aspiration and morphology)

6.2.2.6. Cycle 2, Day 15 (± 3 days)

The following activities will take place during this visit:

- Physical examination
- Vital sign determinations
- Review of concomitant medications
- Collection of samples obtained before dosing for clinical laboratory tests (hematology, chemistry, and urinalysis)
- AE/SAE evaluation
- Review of returned study medication and assessment of compliance

6.2.2.7. Cycle 3, Day 1 (± 3 days)

The following activities will take place during this visit:

- Physical examination
- Vital sign determinations
- ECOG performance status evaluation
- Review of concomitant medications
- 12-lead ECG before dosing and 2 to 4 hours after dosing
- Collection of samples obtained before dosing for clinical laboratory tests (hematology, chemistry, and urinalysis)
- Bone marrow aspiration and biopsy for local determination of response; biopsy may be omitted if the aspirate is considered to be adequate

- AE/SAE evaluation
- Collection of blood samples for PK determinations before dosing and 2 to 4 hours after dosing. When an ECG is performed at the same study time point, the PK specimen should be taken immediately afterwards.
- Administration of quizartinib at the study site
- Review of returned study medication and assessment of compliance

6.2.2.8. Cycle 4 and Subsequent Cycles, Day 1 (±3 days)

The following activities will take place during these visits:

- Physical examination
- Vital sign determinations
- ECOG performance status evaluation
- Review of concomitant medications
- A urine pregnancy test must be performed every 3 months during the treatment phase in women of child-bearing potential
- 12-lead ECG (triplicate)
- Collection of samples obtained before dosing for clinical laboratory tests (hematology, chemistry, and urinalysis)
- Bone marrow aspiration and biopsy for local determination of response; (biopsy may be omitted if the aspirate is considered to be adequate) on Day 1 of Cycle 4 unless subject has achieved a CR, CRp or CRi, in which case bone marrow examination should be every 3 cycles subsequently, at the end of treatment/end of study visit, and as clinically indicated
- AE/SAE evaluation
- Review of returned study medication and assessment of compliance

6.2.3. Schedule of Activities and Assessments for Subjects Receiving Quizartinib After HSCT

6.2.3.1. Cycle 1 (Post-HSCT), Day 1

The following activities will take place during this visit:

- Physical examination
- Vital sign determinations
- ECOG performance status evaluation
- Review of concomitant medications
- 12-lead ECG (triplicate) before dosing and 2 and 4 hours after dosing

- Pregnancy testing; women of childbearing potential must have a negative urine pregnancy test result before the start of study treatment and every 3 months during the treatment phase.
- Collection of samples obtained before dosing for clinical laboratory tests (hematology, chemistry, and urinalysis) (blood draws may be performed the prior day; results should be reviewed before dosing)
- Bone marrow aspiration and biopsy for response determination; biopsy may be omitted if the aspirate is considered to be adequate
- Specimen collection for exploratory assessment of FLT3 mutations using bone marrow (or whole blood if marrow cannot be collected); result of FLT3 test not required for subject to start quizartinib.
- AE/SAE evaluation
- Administration of quizartinib at the study site

6.2.3.2. Cycle 1 (Post-HSCT), Day 8 (±1 day)

The following activities will take place during this visit:

- Physical examination
- Vital sign determinations
- Review of concomitant medications
- 12-lead ECG (triplicate)
- Collection of samples obtained before dosing for clinical laboratory tests (hematology, chemistry, and urinalysis)
- AE/SAE evaluation
- Administration of quizartinib at the study site
- Review of returned study medication and assessment of compliance

6.2.3.3. Cycle 1 (Post-HSCT), Day 15 (±1 day)

The following activities will take place during this visit:

- Physical examination
- Vital sign determinations
- Review of concomitant medications
- 12-lead ECG (triplicate) before dosing (including a determination of whether dose escalation is appropriate)
- Collection of samples obtained before dosing for clinical laboratory tests (hematology, chemistry, and urinalysis)
- AE/SAE evaluation

- Administration of quizartinib at the study site
- Review of returned study medication and assessment of compliance

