- ^c Triplicate ECGs to be obtained at screening; on Day 1 of Cycle 1 before dosing and 2, 4 and 6 hours after dosing; on Day 2 and 8 of Cycle 1 before dosing and 2 to 4 hours after dosing; on Day 15 of Cycle 1 before dosing and 2, 4 and 6 hours after dosing; on Day 1 of Cycles 2 and 3 before dosing and 2 to 4 hours after dosing; and on Day 1 of all subsequent cycles with no time restriction. Following dose escalation, triplicate ECG determinations should be performed at least once weekly for 2 weeks to monitor QTcF prolongation.
- ^d Obtained before dosing. Clinical laboratory evaluations are detailed in Section 8.6, [Table 8](#).
- ^e MUGA scans or ECHO are to be performed at screening on all subjects unless a MUGA scan performed within 1 month of screening revealed LVEF \geq 45%.
- ^f Bone marrow aspiration and biopsy for morphology determination are preferred, but biopsy may be omitted if the aspirate is considered to be adequate. Bone marrow samples are required at screening for central testing (within 14 days prior to randomization; bone marrow examinations outside this window may be acceptable if agreed by the Medical Monitor), on Day 1 of Cycle 2 and Cycle 3, at the early termination/end of treatment visit, and as clinically indicated. Bone marrow assessments will be repeated on Day 1 of each subsequent cycle unless the subject has already achieved CR, CRp, or CRi. In that event, bone marrow testing will be repeated after every 3 subsequent cycles, unless there is evidence of relapse. A central laboratory will review a screening specimen to confirm the diagnosis.
- ^g The following specimens must be collected and sent to Genoptix for central analysis. A bone marrow and peripheral blood sample should be obtained at screening (at approximately the same time) for determination of FLT3-ITD status. A bone marrow sample should be obtained at treatment discontinuation or relapse. The sample may also be tested for FLT3 point mutations and mutations in other AML-associated genes.

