^b Triplicate ECGs to be obtained on Day 1 of Cycle 1 post-HSCT before dosing, 2, and 4 hours after dosing; on Day 8 of Cycle 1 post-HSCT; Day 15 of Cycle 1 before dosing (including a determination of whether dose escalation is appropriate); Day 1 of Cycle 2 post-HSCT and all subsequent cycles. Following dose escalation, triplicate ECG determinations should be performed at least once weekly for 2 weeks to monitor QTcF prolongation.

^c Women of childbearing potential must have a negative urine pregnancy test before the start of study treatment and every 3 months during the treatment phase.

^d Bone marrow aspiration and biopsy for morphology determination are preferred, but biopsy may be omitted if the aspirate is considered to be adequate. Bone marrow samples are required on Day 1 of Cycle 1 post-HSCT (may be taken within 14 days prior to the first dose of study drug; this window may be extended after consultation with the Medical Monitor), on Day 1 of Cycle 4 and every 3 cycles subsequently, at the early termination/end of study visit, and as clinically indicated.

^e A bone marrow sample should be obtained at Day 1 Cycle 1 (may be taken with 14 days prior to dosing) for central determination of FLT3 mutations and mutations in other genes. FLT3 test result is not required to start quizartinib following transplantation.

^f Quizartinib should be taken in the morning.

Table 5 Schedule of Activities and Assessments for Subjects Receiving Salvage Chemotherapy

Activity	Screening (≤14 days from random- ization)	Cycle 1				Cycle 2	
		D 1	D 2 and D 8 ±1	D 15 ±3	D 29 ±14	D 1 ±3	D 15 ±3
Written informed consent	X						
Medical and disease history and demographics	X						
Physical examination	X	X	X	X		X	X
Vital sign determinations	X	X	X	X		X	X
ECOG performance status determination	X	X		X		X	X
Assessment of prior and concomitant medications	X ^a	X	X	X		X	X
Pregnancy test for women of childbearing potential	X ^b	X ^b					
Determination of coagulation profile (PT/INR)	X						
Chest X-rays (posterior/anterior and lateral)	X						
12-lead ECG (triplicate)	X ^c	X ^c	X ^c	X ^c		X ^c	X ^c
Clinical laboratory tests (hematology; chemistry; urinalysis)	X ^d	X ^d	X ^d	X ^d		X ^d	X ^d
MUGA scan or ECHO	X ^e					X ^e	
Bone marrow aspiration or biopsy	X ^f				X ^f		
Collection of bone marrow and whole blood specimen for central laboratory FLT3 mutation determination and other AML-associated mutations	X ^g						
AE/SAE assessment		X	X	X		X	X

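### After HSCT, the Day 15 ECG that decides the Day 16 quizartinib increase is pre-dose only, a modestly more lenient check than the first course makes against the same 450 msec limit

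*Combined protocol and SAP*

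**What the plan says.** **After HSCT.** Section 5.6.4.5 restarts quizartinib at 30 mg (20 mg with a strong CYP3A4 inhibitor) and increases it from Day 16 if QTcF is at or below 450 msec. The Day 15 visit in Section 6.2.3.3 lists "12-lead ECG (triplicate) before dosing (including a determination of whether dose escalation is appropriate"). Table 4 footnote b (Section 5.8) agrees: "Day 15 of Cycle 1 before dosing (including a determination of whether dose escalation is appropriate"). Two other ECG visits fall before the increase. Day 1 (Section 6.2.3.1) has readings pre-dose and at 2 and 4 hours after the first post-transplant dose. The Day 8 triplicate is listed in Table 4 footnote b only as "on Day 8 of Cycle 1 post-HSCT", with no time relative to dose; Section 6.2.3.2 gives none either.

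**First course.** Section 5.6.4.3 requires the average triplicate QTcF to be at or below 450 msec up to and including Day 15. The Day 15 visit in Section 6.2.2.3 specifies "12-lead ECG before dosing and 2, 4, and 6 hours after dosing" and, as its next item, "ECG review to determine if dose escalation is required". Table 3 footnote c matches: "on Day 15 of Cycle 1 before dosing and 2, 4 and 6 hours after dosing". The same visit ties these ECGs to PK sampling: "When an ECG is performed at the same study time point, the PK specimen should be taken immediately afterwards".

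**After the post-HSCT increase.** Table 4 footnote b adds: "Following dose escalation, triplicate ECG determinations should be performed at least once weekly for 2 weeks to monitor QTcF prolongation". Again no time relative to dose is set.

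**The concern.** The same QTcF limit gates the Day 16 increase in both courses, but it is compared with different readings. Exposure is lowest just before a dose. A subject restarting after HSCT could read 450 msec or less pre-dose on Day 15, exceed 450 msec a few hours later, and still be escalated on Day 16. The same values in the first course would fail the rule. The other post-HSCT ECGs do not close this gap: the timed Day 1 readings follow a single dose, and the Day 8 reading may be taken at trough. The weekly ECGs and the dose-reduction rules act only once the dose has been raised.

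What is at stake is a small margin in QT monitoring. The OS analysis, type I error and power are not involved.

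**Working it through.** The plan gives no figure to reproduce. The check asks how much of the Day 15 peak each scheduled ECG sees, and what that means in msec.

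**Inputs from the documents.** Section 3.3: effective half-life about 3 days, about 4-fold accumulation, tmax 1 to 8 hours. Section 5.2.5: about 35% of subjects bridged to HSCT. Section 13.3: 242 quizartinib subjects.

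**Assumptions.** One-compartment model with once-daily dosing; QTcF effect proportional to concentration; peak effect 20-40 msec; pre-dose Day 15 QTcF normal with mean 420-440 and SD 15-20 msec. The documents give no QTcF distribution.

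**Step 1: fraction left after 24 hours, q.** From 4-fold accumulation, 1/(1 - q) = 4, so q = 0.75. From a 72-hour half-life, q = 2^(-1/3) = 0.794.

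**Step 2: Day 15 pre-dose as a share of the Day 15 peak.** With instant absorption this is q(1 - q^14)/(1 - q^15) = 0.747 for q = 0.75 and 0.787 for q = 0.794. With first-order absorption and tmax of 1 to 8 hours it is 0.755-0.841. The overall range is therefore 75-84%.

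**Step 3: the other ECG times, as a share of the same peak (first-order absorption).**

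| ECG | Share of Day 15 peak |
|---|---|
| Day 1, better of 2 h and 4 h | 19-25% |
| Day 8, pre-dose | 66-72% |
| Day 8, 2-4 h | 83-91% |
| Day 15, pre-dose | 76-84% |
| Day 15, 4 h | 96-100% |
| Day 15, anywhere in 2-6 h | 94-100% |

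**Step 4: convert to msec.** Gap = (1 - share) x peak effect. The share missed is 1 - 0.841 = 0.159 to 1 - 0.747 = 0.253.
- 20 msec effect: 3.2-5.1 msec.
- 40 msec effect: 6.4-10.1 msec.

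If AC886, whose profile is flatter, carries half the effect (elimination rate 1, 3 or 10 times the parent's, tmax 2-8 h), pre-dose/peak is 0.860-0.916. The share missed is then 0.084-0.140, or 20 x 0.084 = 1.7 to 40 x 0.140 = 5.6 msec. Over both cases the gap is about 2-10 msec, so a pre-dose reading of exactly 450 corresponds to a peak of about 452-460 msec.

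**Step 5: how often the decision changes.** Share = Phi((450 - mean)/SD) - Phi((450 - gap - mean)/SD).
- Mean 430, gap 5: 0.067 (SD 15) or 0.068 (SD 20).
- Parent-only gaps: lowest 0.014 (mean 420, SD 15, gap 3.2); highest 0.248 (mean 440, SD 15, gap 10). About 1-25%.
- AC886 gaps: lowest 0.007 (mean 420, SD 15, gap 1.7); highest 0.132 (mean 440, SD 15, gap 5.6). About 0.7-13%.

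**Step 6: the population.** 0.35 x 242 = 84.7, so about 85 are expected to reach HSCT. Fewer will restart, because Section 5.6.4.5 sets blood-count and GVHD conditions. The documents do not say how many.

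**The case against.** The case for leaving the schedule alone has real weight.

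- **450 msec is a cautious gate, not a harm threshold.** Dose reduction starts above 480 msec (Section 5.6.4.4), and the Cycle 2 Day 1 rule in Section 5.6.4.3 allows escalation of eligible subjects whose QTcF is not more than 60 msec above baseline. This stands and limits the priority.
- **These subjects have had quizartinib before.** Those treated through Day 15 of the first course already had post-dose ECGs, and Sections 5.6.4.4 and 8.5 bar re-escalation after a Grade 3 QTcF reduction. This stands. Apart from that bar, though, no rule carries earlier QTcF readings into the post-HSCT decision.
- **The dense first-course ECGs also serve PK-QTc sampling**, which Table 4 does not include. That explains a lighter schedule, but not why the one remaining reading is placed at trough.
- **Extra ECGs are allowed at the Investigator's discretion (Section 8.4).** They are not required.
- **The frequencies rest on assumptions** and somewhat overstate the effect, since a Day 1 or Day 8 reading above 450 msec could already stop the increase. This stands.

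Three stronger readings are tempting but unsupported. First, a reader might infer that the protocol contradicts itself; the post-HSCT passages agree with one another. Second, a reader might take Table 2 as the QT cost of going from 30 to 60 mg (maximum change above 60 msec 3% vs 19%, Grade 2 5% vs 14%). That table is by starting dose, 63% of the 30 mg group later escalated to 60 mg and 19% of the 60 mg group to 90 mg (Section 5.2.3), and Grade 3 runs the other way (5% vs 3%). It does not isolate the step. Third, a reader might see a lower post-HSCT standard in the looser phrasing of the Day 15 condition in Section 5.6.4.5. Section 5.6.4.4 uses the same phrasing for subjects who enroll on a strong CYP3A4 inhibitor, so this is drafting only.

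**Conclusion.** The point holds as a small, uncompensated difference in safety monitoring. Before the post-HSCT increase, no timed post-dose ECG near steady state is required, so the 450 msec limit is applied somewhat more leniently than in the first course. That exposure is lowest just before a dose needs only repeated once-daily dosing. The 75-84% figure rests on the Section 3.3 pharmacokinetics and a simple model; the 2-10 msec gap and the shares of changed decisions rest on the assumed peak effect, proportionality and QTcF distribution.

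The subjects affected are those within a few msec of the limit, with peaks still well short of the reduction threshold. The calculation does not show that they would be harmed. This is a cheap improvement of low priority.

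**What to change.** 1. In Section 6.2.3.3 and Table 4 footnote b, take the post-HSCT Day 15 escalation triplicate 2 to 6 hours after dosing (for example at 4 hours) instead of pre-dose.
2. In Section 6.2.3.2 and Table 4 footnote b, take the existing Day 8 triplicate 2 to 4 hours after dosing.

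Neither change adds an ECG or a visit, because quizartinib is already given at the site on post-HSCT Days 8 and 15. The costs are a few hours' wait on site, loss of the pre-dose Day 15 reading, and slightly fewer Day 16 escalations. There is also a practical cost: Table 4 has no post-HSCT Day 16 visit, so the dose decision and the tablet supply must be settled later in the Day 15 visit. If the pre-dose reading is to be kept, the alternative is one added triplicate per restarting subject, 85 or fewer in total.
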